14.4 Graft Rejection

The Clinical study report will discuss any cases of graft rejection if there are any.

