4.4 Risk-Benefit Analysis

There is an unmet medical need that warrants intervention for patients in need of corneal transplants.

For patients with visually significant corneal endothelial dysfunction, the only current alternative is watchful waiting in anticipation of a suitable cornea for transplant for either penetrating (PKP) or selective endothelial keratoplasty (DSAEK, DMEK). Watchful waiting may lead to a loss of vision and a burden on the health care of the patient. Disadvantages of PKP include high rates of graft rejection, poor visual quality resulting from irregular astigmatism as well as susceptibility to trauma and suture complications. Disadvantages of EK (DSAEK and DMEK) include surgical complexity, interface haze formation, increased graft detachment rates and high rates of graft failure. While the current available keratoplasty methods are effective, they are complex procedures that require a supply of donor corneas in a 1:1 ratio.

In order to address this medical need, *in vitro* expansion of human CECs is being evaluated as an alternative. This method to prepare human CECs *in vitro*, which can be transferred to the eye, is used to produce AURN001. Additional benefits of this method include smaller surgical incisions that are utilized to deliver treatment without relying on partial or full-thickness donor corneal tissue as carriers for the endothelial cell graft. Thus, in addition to being able to reach a much higher population of patients in need of corneal transplantation, human CEC injection has the

potential to reduce the risk of surgically induced complications, including corneal irregularities and the risk of post-operative graft detachment and/or dislocation of partial or full thickness corneal grafts, while allowing for the potential of one donor cornea to produce cells to treat many patients. The patient experience is improved post-operatively as positioning is limited to the first few hours following surgery, unlike keratoplasty which limits the patients' mobility for several days. In addition, there is a potential lower risk of graft rejection with AURN001 compared with EK or PKP.

In summary, the benefit-risk assessment is such that continued investigation in a clinical study setting is warranted.

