4 TRIAL DESIGN

4.1 Description of Trial

This is a multicenter, randomized, double-masked, parallel-arm, dose-ranging, Phase 1/2 study of AURN001 in subjects with corneal edema secondary to corneal endothelial dysfunction. The efficacy and safety of AURN001 will be assessed in a clinical trial setting in North America in adult subjects with corneal edema secondary to corneal endothelial dysfunction. Three doses of AURN001 compared with the 2 components of AURN001 separately (*neltependocel* and Y-27632) will be evaluated to assess the contribution of these 2 elements to the efficacy and safety of AURN001.

This trial will enroll approximately 100 subjects in the 5 treatment arms with approximately 20 subjects per arm. A randomized treatment sequence will be assigned. The sponsor will assess the actual enrollment in each arm on an on-going basis throughout the study to maintain a

randomization ratio of 1:1:1:1:1. The sponsor will make adjustments to the randomized treatment sequence and the number of subjects to be treated in each cohort as needed.

The treatment arms are as follows:

[figure not shown]
Table 1 Treatment Assignment Paradigm

Arm	No. of Subjects	Neltependocel Dose	Y-27632 Dose	Endothelial Polishing?
1	20	1.0×10^6	100 μ M	Yes
2	20	5.0×10^5	100 μ M	Yes
3	20	2.5×10^5	100 μ M	Yes
4	20	None	100 μ M	Yes
5	20	1.0×10^6	None	Yes

This study will have a screening period, a surgery/treatment day during which treatment will be administered, and a 12-month observation period. The primary efficacy analysis will be conducted at Month 6. The study will have up to 10 visits with one optional visit: the Screening Visit (Visit 1, -77 days to -7 days); Surgery/Treatment (Visit 2, Day 1); and Follow-up (Visits 3 through 10, Day 2, Week 1, Week 4, and Months 2 (optional), 3, 4.5, 6, 9, and 12, respectively). Unscheduled visits will be allowed, as deemed necessary by the investigator.

This study will be conducted per the schedule shown in Figure 1.

Figure 1 Study Schematic

Assessments can be found in the Schedule of Assessments in Appendix 1.

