4.2.2 Safety Evaluations

- Incidence and severity of ocular treatment-emergent adverse events (TEAEs)
- Incidence and severity of non-ocular TEAEs
- Loss from baseline in BCVA ≥ 15 letters
- Rescue rate and time to rescue

- Graft rejection

The safety evaluations will be based on adverse event (AE) reporting, laboratory findings (clinical chemistry and hematology), and ophthalmic examinations, including Goldmann tonometry, Slit Lamp biomicroscopy, gonioscopy, dilated fundoscopy, and BCVA (as measured by ETDRS).

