4.3 Randomization and Masking

This study will be double-masked and will utilize a randomized treatment sequence model. A computer-generated encrypted read-only randomized treatment sequence schedule will be provided by a biostatistician. The randomized treatment sequence schedule will be managed by unmasked team members responsible for assessing enrollment in each arm to maintain a randomization ratio of 1:1:1:1:1.

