4.4 Trial Treatment

Subjects eligible to be treated will receive a single injection of AURN001 (*neltepedocel* with Y-27632), *neltepedocel* alone, or Y-27632 alone into the anterior chamber of the study eye. The dose of *neltepedocel* will be either 1.0×10^6 , 5.0×10^5 or 2.5×10^5 cells; the dose of Y-27632 will be 100 μ M. The total volume of administration will be approximately 300 μ L.

The injection of study treatment into the study eye will be performed under local anesthesia (administration method at the investigator's discretion). After creating a small incision at the corneal limbus, the corneal endothelium will be polished to a diameter of approximately 8 mm. Study treatment will be injected into the anterior chamber using a 27-gauge needle. Immediately after completion of surgery, subjects will lie face down for approximately 3 hours (± 15 minutes).

For detailed instructions, please refer to the Procedure Manual, which includes sponsor observation language.

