6 GENERAL CONSIDERATIONS

6.1 Data Analysis Conventions

Statistical programming and analyses will be performed using SAS® Version 9.4 or higher.

Summaries for continuous and ordinal variables will include the number of observations (n), arithmetic mean, standard deviation (SD), median, minimum, and maximum. Minima and maxima will be reported with the same precision as the raw values; means and medians will be presented to one additional decimal place than reported in the raw values. Standard deviations will be presented to two additional decimal places than reported in the raw values.

Summaries for discrete variables will include counts and percentages. All percentages will be rounded to one decimal place.

All safety and efficacy summaries will be presented by treatment group and overall, where appropriate, for each study visit. Listings will be sorted by treatment group, subject number, study visit, and parameter, as applicable.

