14 SAFETY ANALYSES

14.1 Adverse Events

Adverse events will be coded using Medical Dictionary for Regulatory Activities (MedDRA) version 26.1.

Treatment-emergent adverse events (TEAEs) are defined as any adverse events that occur during or after the Day 1 injections, or any adverse events that are continuous from the screening but worsen during or after the Day 1 injections.

Ocular and non-ocular TEAEs will be summarized separately. Summary of ocular TEAEs will be separated by study eye and non-study eye.

An overall summary including the number of events and the number and percentage of subjects who experienced at least one TEAE will be presented by treatment group and overall. The overall summary will also include at least one serious TEAE, treatment-related TEAE, treatment-related serious TEAE, TEAE leading to subject discontinuation from the study, and TEAE leading to death.

TEAEs will be summarized by System Organ Class (SOC) and Preferred Term (PT). Subjects are counted only once under each SOC or PT for which they have at least one TEAE.

Summaries by relationship to study product, by relationship to study procedure and by maximum severity will also be provided.

Serious TEAEs will not be summarized in table format as it is anticipated number of serious TEAEs will be very limited.

In addition, the following AE summaries will be provided for AEs collected at and after rescue visits:

- Overall summary of TEAE
- TEAE by SOC and PT

For these summaries, denominators to be used for percentage calculation will be number of Rescued subjects.

All AEs will be presented in a subject listing with a flag indicating TEAE and a flag indicating AEs occurred at and after rescue visits. In addition, all serious AEs will be presented in a separate listing.

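### Graft rejection is a listed safety evaluation, but SAP 14.4 plans only a narrative, with no count, percentage or interval by arm or for pooled cell-treated eyes

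*SAP*

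**What the plan says.** SAP 4.2.2 lists "Graft rejection" as one of five safety evaluations, beside ocular adverse events, non-ocular adverse events, loss of 15 or more letters, and rescue. Protocol 6.2.2 does the same. Protocol 4.4.1 names rejection and failure of the graft among the product's risks, and Protocol 4.4 offers as a possible advantage that "there is a potential lower risk of graft rejection with AURN001 compared with EK or PKP".

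The analysis section, SAP 14.4, is one sentence: "The Clinical study report will discuss any cases of graft rejection if there are any". The sections before it plan more. SAP 14.2 gives numbers and percentages with vision loss at each visit, by group and overall. SAP 14.3 gives rescue counts, a median time with 95% interval, and Kaplan-Meier plots.

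The layout of the tables is set in SAP 6.1: "All safety and efficacy summaries will be presented by treatment group and overall, where appropriate, for each study visit". SAP 14.1 adds that ocular treatment-emergent adverse events (TEAEs) are tabulated for the study eye by system organ class and preferred term, and that every AE is listed by subject.

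On size, SAP 4.1 states: "This trial will enroll approximately 100 subjects in the 5 treatment arms with approximately 20 subjects per arm". SAP 4.3 gives a "randomization ratio of 1:1:1:1:1". Arms 1, 2 and 3 receive cells with Y-27632, and Arm 5 receives cells alone. Arm 4 receives no cells, only "Y-27632 alone into the anterior chamber of the study eye".

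**The concern.** Graft rejection is the only one of the five listed safety evaluations whose own section plans no summary. SAP 7.3 gives the study's purpose as providing initial estimates of the endpoints for later trials. A narrative of whatever cases turn up is not an estimate, because it has no stated numerator rule, denominator or interval.

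This matters most if few or no cases are seen. The report could then say that little or no rejection occurred without showing how high a rate the data still allow. Rejection also carries part of the benefit-risk argument in Protocol 4.4, so the uncertainty should be visible.

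The one pooled column in the planned tables adds a smaller problem: it puts subjects who received no cells into the denominator for an event that concerns the cells.

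**Working it through.** **Inputs.** SAP 4.1 and Table 1 plan 5 arms of about 20. The total is 5 × 20 = 100, which reproduces the stated figure. Eyes receiving any cells (Arms 1, 2, 3, 5): 4 × 20 = 80. Eyes receiving AURN001, meaning cells plus Y-27632 (Arms 1 to 3): 3 × 20 = 60. No expected rejection rate and no precision target for safety is given. The interval method is borrowed from SAP 13.1.1, which uses two-sided exact Clopper-Pearson 95% limits for the primary endpoint.

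**Zero cases.** The upper limit is 1 − 0.025^(1/n). The last three columns give the chance of seeing at least one case, 1 − (1 − p)^n, at assumed true rates p of 1%, 2% and 5%.

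| Group | n | Upper limit, 0 cases | p = 1% | p = 2% | p = 5% |
|---|---|---|---|---|---|
| One arm | 20 | 16.8% | 18.2% | 33.2% | 64.2% |
| AURN001 (Arms 1–3) | 60 | 6.0% | 45.3% | 70.2% | 95.4% |
| Any cells (Arms 1, 2, 3, 5) | 80 | 4.5% | 55.2% | 80.1% | 98.3% |
| Overall, Arm 4 included | 100 | 3.6% | n/a | n/a | n/a |

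The last row has no detection figures because Arm 4 receives no cells to reject.

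**Some cases.** If all cases fall in cell-treated eyes, the *overall* column shows 80/100 = 0.80 of their rate. Four cases are 4/80 = 5.0% (95% CI 1.4% to 12.3%) among cell-treated eyes, but 4/100 = 4.0% (1.1% to 9.9%) in *overall*.

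**Can the AE tables fill the gap?** A rejection recorded as an ocular TEAE would be counted by preferred term and arm (SAP 6.1 and 14.1, Protocol 10.8), and the arms could be added by hand. Three things weaken that route:

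- Neither document says what counts as rejection of injected cells, or whether rejection of a donor graft placed at rescue is included.
- Protocol 9.3 excludes clinical findings associated with lack of efficacy from AEs. A rejection that presents as returning edema could be read that way and not be recorded as an AE.
- SAP 7.9 and 14.1 take AEs at and after rescue visits out of the main tables and summarize them separately, with rescued subjects as denominator. The numerator can therefore split. As an illustration, if two of four cases were recorded at the rescue visit, the main tables would support 2/80 = 2.5% (0.3% to 8.7%) instead of 4/80 = 5.0%. The other two would appear over a different denominator.

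**The case against.** The strongest reply is that nothing is lost. Rejection is a named product risk and fits the protocol's AE definition. Counts by arm would appear in the preferred-term tables, and every case would be listed. If the report says there were none, any reader can work out the 4.5% limit from the arm sizes. The study is descriptive, and vision loss, the other binary safety endpoint, has no interval either.

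Much of this stands. A reader might infer that the trial yields no usable rejection rate for cell-treated eyes. The documents do not support that: the data can give one, and the planned tables would give most of it if rejection is recorded as an AE before rescue. The defect lies in planned reporting. What the reply leaves open is the case rule, the lack-of-efficacy exclusion and the separate rescue table. A descriptive aim does not argue against an exact interval, which needs no hypothesis test.

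A reader might also infer that the *overall* column dilutes every cell-related risk by one fifth. It does so only for events that cannot occur in Arm 4. That arm also has endothelial polishing, the injection and Y-27632, and Protocol 4.4.1 lists events such as uveitis and raised pressure under surgery as well as under the product. The *overall* column is also shown only where appropriate, beside the arm columns.

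Nor is it safe to say that no Arm 4 eye can reject a graft. Rescue is by keratoplasty, so a rescued Arm 4 eye would hold donor tissue. This is one more reason to define the event.

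Finally, the pool of 80 does not match the statement in Protocol 4.4, which concerns AURN001. Arm 5 is cells without Y-27632, and Protocol 4.5 reports meaningfully diminished activity, including on need for rescue, with cells alone. The matching pool is Arms 1 to 3, n about 60. With no EK or PKP arm, neither pool can by itself establish a lower risk than keratoplasty.

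**Conclusion.** The point holds as a gap in planned reporting of a listed safety evaluation. The column choice alone has a modest and calculable effect: with no cases, 3.6% in *overall* against 4.5% for any cells and 6.0% for AURN001. A single arm of 20 says little, since its limit is 16.8%. The less predictable part is the numerator, because a case may go unrecorded as an AE or move to the rescue table, and the documents give no means of sizing that.

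The figures rest on planned arm sizes, which SAP 4.1 calls approximate and lets the sponsor adjust. The 0.80 factor assumes that all cases are in cell-treated eyes. The 1% to 5% rates and the two-of-four split are illustrations.

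**What to change.** Rewrite SAP 14.4, before the Month 6 unmasking, to:

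- state which recorded events count as rejection of the injected cells, and report rejection of a rescue keratoplasty graft separately;
- give number, percentage and Clopper-Pearson 95% interval through Month 6 and through Month 12;
- show these by arm, for AURN001 (Arms 1 to 3), and for any cells (Arms 1, 2, 3 and 5);
- count cases identified up to and including the rescue visit, as a stated exception to SAP 7.9, with all treated subjects in those arms as denominator.

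The cost is some SAP wording and one small table. Pooling assumes similar risk across cell doses and with or without Y-27632, so the per-arm columns must stay. An any-cells column in the other ocular TEAE tables is optional.

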14.5 Slit-lamp Examination

Slit-lamp examination data will be summarized by visit and by eye, and a subject listing will be presented.

14.6 Gonioscopy

Gonioscopy data will be summarized by visit and by eye, and a subject listing will be presented.

14.7 Dilated Fundus Ophthalmoscopy

Dilated fundus ophthalmoscopy data will be summary by visit and by eye, and a subject listing will be presented.

14.8 Spectral Domain Optical Coherence Tomography

Spectral Domain Optical Coherence Tomography (SD-OCT) macula data will be summarized by visit and by eye, and a subject listing will be presented.

14.9 Intraocular Pressure

The observed and change from Baseline in IOP will be summarized for study eye and non-study eye separately using continuous descriptive statistics at each post-baseline visit by treatment group and overall.

The number and percent of subjects with a ≥ 10 mmHg increase from baseline and the number and percent of subjects with a ≥ 30 mmHg observed value will be presented.

Post-baseline IOP data will be presented in a listing, along with flags indicating a ≥ 10 mmHg increase from baseline and a ≥ 30 mmHg observed value.

IOP data will be presented in a listing.

14.10 Clinical Laboratory Data

Clinical laboratory testing will include clinical chemistry and hematology evaluations. The quantitative variables and change from baseline will be summarized by treatment group and overall by study visit using continuous descriptive statistics. The counts and percentages of qualitative variables will be summarized by treatment group and overall by study visit.

Clinical laboratory results will be presented in a listing.

14.11 Urine Pregnancy Test

Urine pregnancy tests will be presented in a listing.

15 CHANGES FROM PROTOCOL-STATED ANALYSES

There are no changes to the protocol-stated analyses.

16 REVISION HISTORY

Documentation of revision to the SAP will commence after approval of Final version 1.0.

